3.11. Interim Analyses

There is no formal interim analysis planned for this study. Interim data examinations may be performed, but these will be of a descriptive nature and will not involve any formal hypothesis testing. In particular, summaries of changes from baseline for clinical activity parameters will be conducted on the 6, 12, 18, and 24 month data.

4. STUDY ANALYSES

4.1. Subject Disposition

Subject disposition will be tabulated and include the number enrolled, the number dosed with patisiran, the number who completed the study, the number in each subject population for analysis, the number who withdrew prior to completing the study and reason(s) for withdrawal.

A by-subject data listing of study completion information including the reason for premature study withdrawal will be presented.

4.2. Demographics and Baseline Characteristics

Demographics, baseline characteristics, and medical history information will be summarized for the Full Analysis Set and Cardiac Subgroup.

Age, height, weight, BMI, albumin, and mBMI will be summarized using descriptive statistics (number of subjects, mean, SD, median, minimum, and maximum). Sex, race, ethnicity, and country will be summarized by presenting the numbers and percentages of subjects in each category. The numbers of subjects included in the PK/PD and cardiac subgroup will also be summarized.

Baseline disease characteristics will be summarized, including the time since diagnosis with ATTR, and the numbers and percentages of subjects

- V30M or other mutation
- FAP stage (0, I, II, III)
- PND score (0, I, II, IIIA, IIIB, IV)
- Karnofsky Performance Status (\leq 60, 70-80, 90-100)
- New York Heart Association class (I, II, III, IV)
- Concomitant TTR stabilizer (yes or no)

Baseline clinical activity parameters including NIS, mNIS+7, NIS+7, EQ-5D, R-ODS, COMPASS-31, 10-meter walk test, and grip strength test scores will also be summarized.

Baseline data will be also be summarized for Cardiac Subgroup separately.

All demographic and baseline data for each subject will be provided in data listings.

Medical history will be summarized by system organ class (SOC), high level terms (HLT), and preferred terms. Medical history and prior surgeries will be presented in a data listing. Pregnancy test results will be presented in data listings.

Any data from former neurological test scores will be presented in a data listing.

4.3. Pharmacodynamic Analysis

The following biomarkers will be evaluated for assessment of the PD effect of patisiran:

- TTR protein
- Retinol binding protein (RBP)
- Vitamin A

PD analyses will use the Full Analysis Set. Summary statistics for each PD parameter will be presented. Serial measurements, changes and percentage changes from baseline will be summarized for each scheduled time point using descriptive statistics. Maximum and mean TTR % reduction from baseline over 24 months will be summarized. Mean TTR % reduction from baseline will be calculated using all TTR values on or after Day 8. Mean TTR % reduction will also be calculated for all pre-dose (within 1 hour of planned dosing start) visits.

In addition, serial TTR will be summarized by genotype (V30M versus non-V30M), stabilizer use (yes versus no), gender (female versus male), and age (<65 versus \geq 65 years old).

TTR levels over time will be plotted. Each subject's TTR levels will be joined by a line. Group means (with standard error bars) for observed values and percent change from baseline will be plotted over time. Similar plots will be produced for RBP and Vitamin A.

The post-hoc non-native TTR analysis will also be summarized.

4.4. Summary of Clinical Activity Assessments

The following clinical activity assessments will be collected:

- Neurologic impairment will be assessed using the mNIS + 7 composite score, consisting of the NIS weakness and reflex domains, 5 nerve conduction studies (Σ 5 NCS), quantitative sensory testing (QST) by body surface area including touch pressure (TP) and heat pain (HP), as well as autonomic assessment through postural blood pressure. A scoring algorithm, including methods for handling missing components of the mNIS+7, is included in Section 7.1.
- The NIS score (i.e., the sum of cranial nerve, muscle weakness, reflex and sensation scores) will also be assessed.
- Neurologic impairment will also be assessed by NIS+7 [19]. The NIS+7 includes the full NIS, sum of five NCS (overlapping but not identical to the Σ 5 NCS calculated for mNIS+7 above, vibration detection threshold [VDT], and heart rate response to deep breathing [HRdb]). A scoring algorithm for the NIS+7 is included in Section 7.1.
- Patient reported QOL will be evaluated using the EQ-5D index value (using U.S. references to calculate the index). Categorical summaries of each EQ-5D domain will be provided. Overall health will be assessed by the EQ-VAS. Disability will be reported by patients using the R-ODS. Scoring algorithms for the EQ-5D and R-ODS are included in Section 7.2 and Section 7.3.
- Motor function assessments will include a timed 10-meter walk test and test of grip strength in dominant arm, as well as an evaluation of ambulation using PND score and FAP stage.
- Pathologic evaluation of sensory and autonomic innervation will be evaluated by IENFD analysis and quantitation of SGNFD via tandem 3 mm skin punch biopsies taken from the leg and thigh.
- Nutritional status of patients will be evaluated using the mBMI, calculated as BMI (kg/m^2) multiplied by albumin (g/L).

- To evaluate patient reported autonomic neuropathy symptoms, patients will complete the COMPASS 31 questionnaire, consisting of 31 clinically selected questions which evaluate 6 autonomic domains [1]. A scoring algorithm for the COMPASS-31 total score and domain scores is included in Section 7.4.
- Magnetic resonance neurography (MRN) of peripheral nerves in the lower extremity and lumbar plexus will be performed for consenting patients.

Analyses of clinical activity assessments will use the Full Analysis Set. Summary statistics of observed values and changes from baseline will be provided for the mNIS+7 composite score. Summaries will also be provided for the components of the composite score (i.e., the NIS weakness and reflex scores, the Σ 5 NCS, QST values, and postural blood pressure). The full NIS (i.e., the sum of cranial nerve, muscle weakness, reflex and sensation scores) and NIS+7 will also be summarized overall and by component as above.

Patient reported autonomic neuropathy symptoms will be assessed by descriptive statistics for the COMPASS 31 (including overall and domain scores).

Descriptive statistics will also be provided for observed values and changes from baseline in motor function (10-meter walk test speed and grip strength), nutritional status (mBMI), sensory and autonomic innervation (IENFD and SGNFD), and ambulation (FAP stage and PND score).

The above clinical activity parameters will be summarized overall, by stabilizer use (any versus none), and by Cardiac Subgroup versus all others. The mNIS+7 composite score and component scores will also be summarized by baseline age (<65 vs \geq 65) and gender.

4.4.1. Association between TTR Reduction and Clinical Activity

The therapeutic hypothesis for patisiran is that TTR reduction will result in clinical benefit in hATTR-PN patients. The inter-patient variability in the degree of TTR reduction at 0.3 mg/kg provides an opportunity to examine the relationship of TTR reduction to change in neuropathy progression as measured by mNIS+7. TTR reduction 17 days after the first dose of patisiran (Day 18 %TTR Reduction) was chosen for analysis of the correlation between TTR reduction and change in mNIS+7 because it reduces the impact of missed doses or missed TTR assessments over 24 months of dosing.

Pearson correlation coefficients will be calculated for Day 18 TTR % reduction and mNIS+7 change from baseline (including total score and component scores) at each of the 6, 12, 18, and 24 month time points. Scatterplots will be provided to visualize the data.

4.4.2. Associations among Baseline Clinical Activity Parameters

Associations among baseline clinical activity parameters will also be explored. Pearson correlation coefficients will be calculated to evaluate the linear relationship among continuous variables (e.g. mNIS+7 versus NIS+7, mNIS+7 versus EQ-5D index score, etc.). Spearman correlation coefficients will be calculated for a continuous variable versus a nominal variable or for two nominal variables (e.g. FAP stage and mNIS+7, PND score and NIS). Scatterplots will be provided to visualize the data.

4.5. Pharmacokinetic Analysis

PK analysis will be conducted in the PK analysis set.

4.5.1. Study Variables

4.5.1.1. Concentration Data

Urinary concentrations of ALN-18328 (siRNA) and 4-dimethylaminobutyric acid, as well as plasma concentrations of ALN-18328, DLin-MC3-DMA and PEG₂₀₀₀-C-DMG will be obtained. Concentration values that are below the limit of quantification (LLOQ or BLQ) will be set to zero for analysis.

4.5.1.2. Plasma ALN-TTR02 Pharmacokinetic Parameters

Pharmacokinetic parameters to be calculated include:

- Observed trough concentration (C_{trough})
- Observed maximum concentration (C_{max})
- Time of observed maximum concentration (T_{max})
- Area under the plasma concentration-time curve within a dosing interval (AUC(τ))
- Elimination half-life (t_{1/2 beta}) and t_{1/2 alpha})
- Systemic clearance (CL)
- Volume of distribution at steady state (V_{ss})
- Volume of distribution based on the terminal phase (V_z)

4.5.2. Statistical Methods

Descriptive statistics for plasma and urine concentration and plasma PK parameters will include the number of subjects, mean, standard deviation (SD), coefficient of variation (CV), median, minimum, and maximum.

The plasma concentrations of ALN-18328 (siRNA), DLin-MC3-DMA and PEG₂₀₀₀-C-DMG as well as urinary ALN-18328 and 4-dimethylaminobutyric acid concentrations data will be summarized at each nominal time point. Mean concentrations (+SD) as well as individual concentrations will be plotted versus nominal sampling time on a log-linear scale.

The PK parameters will be summarized for ALN-18328 (siRNA), DLin-MC3-DMA and PEG₂₀₀₀-C-DMG. C_{trough} and C_{max} will be summarized for Days 22, 43, 64, 85, 169, 274, 358, 463, 547, 673, and 736. The following parameters will be summarized for Day 1: C_{max}, C_{trough}, T_{max}, and AUC(τ); for Day 232: C_{max}, C_{trough}, and T_{max}; for Day 726: C_{max}, C_{trough}, T_{max}, t_{1/2 alpha}, t_{1/2 beta}, CL, V_{ss}, and V_z.

Plasma concentration data and PK parameters will be presented in by-subject listings.

The relationship between exposure to ALN-18328 (C_{max}) and the extent of reduction of TTR protein, vitamin A and RBP will be explored graphically. Mixed-effects models may be used to assess the relationship between exposure to ALN-18328 and the reduction of TTR protein, vitamin A, and RBP.

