- s The following premedications will be administered at least 60 minutes prior to the start of the infusion of ALN-TTR02: dexamethasone (10 mg IV, or equivalent), paracetamol (PO 500 mg; or equivalent), IV H2 blocker (e.g., ranitidine 50 mg, famotidine 20 mg, or equivalent other H2 blocker dose), and IV H1 blocker (e.g., diphenhydramine 50 mg or equivalent; hydroxyzine or fexofenadine 25 mg PO or cetirizine 10 mg PO may be substituted for any patient who does not tolerate IV diphenhydramine or other IV H1 blockers).
- t The infusion site will be assessed for any localized reaction pre-dose, during the infusion, at the end of the infusion (EOI), and for 30 minutes after the infusion.
- u Plasma PK samples will be collected pre-dose (within 1 hour of planned dosing start; -5 minutes), EOI (+5 minutes), and 1 hour post-dose (± 5 min), except on Days 0 and 231 for subjects in the PK/PD Subgroup. The EOI will usually occur at 70 minutes after the start of the infusion, except in patients where the infusion has been prolonged. All post-infusion times are relative to the EOI, regardless of the duration of the infusion. In addition, if the infusion is stopped and the site is considering restarting the infusion, a PK blood sample will be taken while the infusion is stopped.
- v Samples to be collected on Day 0, 21, 42 and 63 only.
- w Samples will be collected once on each day of the 2-day study visit.
- x For each dose, urine PK samples will be collected pre-dose (within 1 hour of planned dosing start; -5 minutes) and 1 hour (± 5 minutes) after dosing with ALN-TTR02.
- y For patients in the PK/PD subgroup, blood samples for TTR, RBP, and vitamin A will be collected on Days 0 and 231 immediately prior (within 10 minutes) to administration of premedications. In addition, a TTR, RBP, and vitamin A sample will also be collected 24 hours (± 120 minutes) post-dose, and 3, 7, and 17 days (± 1 day) after dosing with ALN-TTR02 for the study visits noted (blood samples for TTR will not be collected on Days 42 and 189).

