- p The following premedications will be administered at least 60 minutes prior to the start of the infusion of ALN-TTR02: dexamethasone (10 mg IV, or equivalent), paracetamol (PO 500 mg; or equivalent), IV H2 blocker (e.g., ranitidine 50 mg, famotidine 20 mg, or equivalent other H2 blocker dose), and IV H1 blocker (e.g., diphenhydramine 50 mg or equivalent; hydroxyzine or fexofenadine 25 mg PO or cetirizine 10 mg PO may be substituted for any patient who does not tolerate IV diphenhydramine or other IV H1 blockers).
- q The infusion site will be assessed for any localized reaction pre-dose, during the infusion, at the end of the infusion and for 30 minutes after the infusion.
- r Plasma PK samples will be collected pre-dose (within 1 hour of planned dosing start; -5 minutes) and at EOI (+5 minutes). In addition, if the infusion is stopped and the site is considering restarting the infusion, a PK blood sample will be taken while the infusion is stopped. In addition, plasma samples will be collected once on each day of the Mid-year and Annual visits.
- s For each dose, urine PK samples will be collected 1 hour postdose (± 5 minutes).
- t For patients in the PK/PD subgroup, blood samples for TTR, RBP, and vitamin A will be collected on Day 735 immediately prior (within 10 minutes) to administration of premedications. In addition, a TTR, RBP, and vitamin A sample will also be collected 24 hours (± 120 minutes) post-dose, and 3, 7, and 17 days (± 1 day) after dosing with ALN-TTR02 for the study visit noted.
- u On Day 735, patients in the PK/PD subgroup will have PK samples taken pre-dose (within 1 hour of planned dosing start; -5 minutes), EOI (+5 minutes), and 1, 2, 4, 6, and 24 hours post-infusion. In addition, a plasma PK sample will also be collected 3, 7, and 17 days (± 1 day) after dosing with ALN-TTR02 for the study visit noted. The windows for sampling are ± 5 minutes for the 1, 2, 4, and 6 hour sampling periods; and ± 120 minutes for the 24 hour sampling period.
- v On Day 735, patients in the PK/PD subgroup will have a urine sample for PK analysis taken pre-dose (within 1 hour of planned dosing start; -5 minutes), EOI (+5 minutes), and 6 and 24 hours post-infusion. In addition, a urine PK sample will also be collected 3, 7, and 17 days (± 1 day) after dosing with ALN-TTR02 for the study visit noted. The windows for sampling are ± 5 minutes for the 1, 2, 4, and 6 hour sampling periods; and ± 120 minutes for the 24-hour sampling period.

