6.2.1.3 Post-dose

Patients will remain at the study site for at least 1 hour following completion of dosing for the following assessments:

- Collect blood samples for PK analyses at EOI and 1 hour post-dose for the first dose and every dose up through, and including, the 3 month dosing visit, and then on 6, 9, and 12 month dosing days. Collect blood samples for PK analyses at EOI (+5 minutes) on 15, 18, 21, and 24 month dosing days. If the infusion is stopped and the site is considering restarting the infusion, a PK blood sample will be taken while the infusion is stopped.
- Collect urine for PK at 1 hour post-dose for the first dose and every dose up through, and including, the 3 month dosing visit, and then every 6, 9, 12, 15, 18, 21, and 24 month dosing days.
- Document any AEs, beginning with the initiation of the first infusion.
- Obtain concomitant medications information.

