7.5.1 Plasma Pharmacokinetics

The PK evaluation will include plasma-concentration time profiles for siRNA and the novel lipid components DLin-MC3-DMA and polyethylene glycol (PEG)₂₀₀₀-C-DMG. Details of the PK evaluation and analysis will be described in the PK and PK/PD analysis plan.

Plasma and urine samples will be evaluated using a validated ATTO-Probe-HPLC assay to determine siRNA concentration and by LC/MS/MS for DLin-MC3-DMA and PEG₂₀₀₀-C-DMG concentrations.

Blood sample collection times are included in the schedule of events (see Table 1-1 and Table 1-2 or Table 12-1 and Table 12-2). For all patients, plasma PK samples will be collected pre-dose (within 1 hour of planned dosing start) EOI and 1 hour post-dose at first dose and every dose up through, and including, the 3 month dosing visit, and then at 6, 9, and 12 month dosing days. Plasma PK samples will be collected pre-dose (within 1 hour of planned dosing start) and EOI at 15, 18, 21, and 24 month visits. The EOI will usually occur at 70 minutes after the start of the infusion, except in patients where the infusion has been prolonged. In addition, if the infusion is stopped and the site is considering restarting the infusion, a PK blood sample will be taken while the infusion is stopped. All PK samples will be collected according to the schedule of assessments when the dose is completed (i.e., all post-infusion times are relative to the EOI, regardless of the duration of the infusion). Plasma PK samples will also be collected at the Mid-year and Annual visits (1 sample collected on each of the 2 study visit days), the 21- and 56-day Follow-up visits, and the Early Termination visit.

For the PK/PD subgroup subjects, samples will be collected pre-dose, and at 1, 2, 4, 6, and 24 hours post-infusion; and at 3, 7 and 17 days post-dose for the first dose and the 8 and 24 month dosing days.

Pharmacokinetic analyses will consist of either a noncompartmental and/or compartmental analysis of plasma siRNA, DLin-MC3-DMA (lipid), and PEG₂₀₀₀-C-

DMG (lipid). Details of the PK evaluation and analysis will be described in the PK and PK/PD analysis plan. Pharmacokinetic parameter estimates to be calculated may include, but may not be limited to:

- Observed C_{max} .
- Time of observed maximum concentration (t_{max}).
- Partial area under the plasma concentration-time curve (AUC_p).
- Area under the plasma concentration-time curve to the last measurable concentration (AUC_{0-t}).

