- p The following premedications will be administered at least 60 minutes prior to the start of the infusion of ALN-TTR02: dexamethasone (10 mg IV, or equivalent), paracetamol (PO 500 mg; or equivalent), IV H2 blocker (e.g., ranitidine 50 mg, famotidine 20 mg, or equivalent other H2 blocker dose), and IV H1 blocker (e.g., diphenhydramine 50 mg or equivalent; hydroxyzine or fexofenadine 25 mg PO or cetirizine 10 mg PO may be substituted for any patient who does not tolerate IV diphenhydramine or other IV H1 blockers).
- q The infusion site will be assessed for any localized reaction pre-dose, during the infusion, at the end of the infusion and for 30 minutes after the infusion.
- r Plasma PK samples will be collected pre-dose (within 1 hour of planned dosing start; -5 minutes) and at EOI (+5 minutes). In addition, if the infusion is stopped and the site is considering restarting the infusion, a PK blood sample will be taken while the infusion is stopped. In addition, plasma samples will be collected once on each day of the Mid-year and Annual visits.
- s For each dose, urine PK samples will be collected 1 hour postdose (\pm 5 minutes).
- t For patients in the PK/PD subgroup, blood samples for TTR, RBP, and vitamin A will be collected on Day 735 immediately prior (within 10 minutes) to administration of premedications. In addition, a TTR, RBP, and vitamin A sample will also be collected 24 hours (\pm 120 minutes) post-dose, and 3, 7, and 17 days (\pm 1 day) after dosing with ALN-TTR02 for the study visit noted.
- u On Day 735, patients in the PK/PD subgroup will have PK samples taken pre-dose (within 1 hour of planned dosing start; -5 minutes), EOI (+5 minutes), and 1, 2, 4, 6, and 24 hours post-infusion. In addition, a plasma PK sample will also be collected 3, 7, and 17 days (\pm 1 day) after dosing with ALN-TTR02 for the study visit noted. The windows for sampling are \pm 5 minutes for the 1, 2, 4, and 6 hour sampling periods; and \pm 120 minutes for the 24 hour sampling period.

- v On Day 735, patients in the PK/PD subgroup will have a urine sample for PK analysis taken pre-dose (within 1 hour of planned dosing start; -5 minutes), EOI (+5 minutes), and 6 and 24 hours post-infusion. In addition, a urine PK sample will also be collected 3, 7, and 17 days (± 1 day) after dosing with ALN-TTR02 for the study visit noted. The windows for sampling are ± 5 minutes for the 1, 2, 4, and 6 hour sampling periods; and ± 120 minutes for the 24-hour sampling period.

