3.10. Visit Windows

It is expected that all visits should occur according to the protocol schedule. All data will be tabulated and analyzed per the evaluation visit as recorded on the electronic case report form (eCRF) even if the assessment is outside of the visit window. In data listings, the relative day of all dates will be presented.

Data collected at unscheduled visits will be included in by-subject data listings and figures, but no assignment to a study visit will be made for the purpose of by-visit summary tabulations. However, unscheduled visits will be considered for baseline values, as discussed in Section 3.4, and for inclusion in any categorical shift summaries (e.g., shift from baseline to “worst” post-baseline value). In addition, summaries of PD parameters (serum TTR, vitamin A, and RBP) will include separate tables and figures using All Data and Scheduled Visits Only.

Note that in the protocol Schedule of Assessments, the first dose day is designated as Day 0. In the SAP, the first dose day will be defined as Day 1 as specified in Section 3.2. In all tables, figures, and listings, on-treatment study days will equal to reported visit days + 1.

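### Observed Cmax is tabulated as one two-year series, but the post-infusion samples behind it differ between Year 1, Year 2 and the Month-24 rich profile, so the visits are not comparable

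*SAP*

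**What the plan says.** SAP 4.5.1.2 defines Cmax as "Observed maximum concentration", with no fixed set of sampling times. SAP 4.5.2 then lists the visits for Ctrough and Cmax, which "will be summarized for Days 22, 43, 64, 85, 169, 274, 358, 463, 547, 673, and 736". SAP days run one ahead of protocol days (SAP 3.10: "In all tables, figures, and listings, on-treatment study days will equal to reported visit days + 1").

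The sampling schedule for every-3-week dosing is:

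- **Year 1, routine PK visits.** Protocol Table 1-1, footnote u, has a pre-dose sample, then "EOI (+5 minutes), and 1 hour post-dose (± 5 min), except on Days 0 and 231 for subjects in the PK/PD Subgroup". Protocol 6.2.1.3 agrees: "Collect blood samples for PK analyses at EOI and 1 hour post-dose for the first dose and every dose" up to and including Month 3, then Months 6, 9 and 12.
- **Year 2, routine PK visits.** Protocol Table 1-2, footnote r: "Plasma PK samples will be collected pre-dose (within 1 hour of planned dosing start; -5 minutes) and at EOI (+5 minutes"). Protocol 7.5.1 agrees: "Plasma PK samples will be collected pre-dose (within 1 hour of planned dosing start) and EOI at 15, 18, 21, and 24 month visits".
- **Month 24, PK/PD subgroup.** SAP Table 1-2, footnote u: "On Day 735, patients in the PK/PD subgroup will have PK samples taken pre-dose", then at EOI and at 1, 2, 4, 6 and 24 hours, with later samples on Days 3, 7 and 17 after the dose.

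The SAP's PK Analysis Set (SAP 2.1) needs only enough data for one key PK parameter, so sparsely sampled patients can enter these tables. SAP 4.5.2 also names Cmax as the exposure measure in the graphs against reduction of TTR, vitamin A and RBP.

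**The concern.** A maximum over more samples is never smaller than a maximum over a subset of them. A by-visit Cmax series is comparable over time only if every visit draws on the same nominal times, and here it does not. The SAP neither restricts Cmax to common times nor mentions the change.

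This is a long-term dosing study, and the repeated Cmax series is where a reader would look to see whether peak exposure is stable over two years. A change in sampling could show as a fall in peak exposure after Year 1, or hide part of a real increase. On Day 736 the direction of any step also depends on who is in the PK/PD subgroup. If Cmax values from both years are plotted against TTR, RBP or vitamin A reduction, the same non-comparability enters those plots.

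**Working it through.** The plan states no figure on this point, so there is none to reproduce.

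**1. Samples behind Cmax on each listed day** (SAP day = protocol day + 1; pre-dose is common to all)

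| SAP days | Post-infusion samples, routine | PK/PD subgroup |
|---|---|---|
| 22, 43, 64, 85, 169, 274, 358 | EOI, 1 h | same |
| 463, 547 | EOI | same |
| 673 | none scheduled on this day (step 5) | same |
| 736 | EOI | EOI, 1, 2, 4, 6, 24 h |

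Seven of the 11 listed days are in Year 1 and four in Year 2. At full planned numbers, the patients on Day 736 with EOI only are 28 − 19 = 9 (SAP 3.1) or 28 − 25 = 3 (Protocol 9.1).

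**2. Direction.** For one fixed profile, max(pre, EOI) ≤ max(pre, EOI, 1 h). The sparse Year 2 value is equal or lower, and adding patients does not average this out. On Day 736 the subgroup's maximum has more chances to be high than on any routine Year 1 day.

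**3. Size, under assumptions.** Let D = ln(C at 1 h / C at EOI) be Normal with mean μ = ln r and SD s. Neither r nor s is in the documents. Dropping the 1-hour sample multiplies geometric-mean Cmax by exp(−E), where E = μΦ(μ/s) + sφ(μ/s).

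- Example, r = 1.0, s = 0.2: E = 0.2 × 0.3989 = 0.0798; the drop is 1 − exp(−0.0798) = 7.7%.

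| r | s = 0.1 | s = 0.2 | s = 0.4 |
|---|---|---|---|
| 0.5 | 0.0% | 0.0% | 0.7% |
| 0.7 | 0.0% | 0.3% | 4.0% |
| 0.8 | 0.0% | 1.3% | 7.0% |
| 0.9 | 0.7% | 3.7% | 10.6% |
| 1.0 | 3.9% | 7.7% | 14.7% |
| 1.1 | 9.9% | 12.7% | 19.1% |

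The SAP plans arithmetic means, so I also took EOI and 1-hour values as log-normal with equal CV. The mean of the larger then exceeds mean EOI by Φ(s/2 − ln r/s) + rΦ(s/2 + ln r/s) − 1, where r is now the ratio of means, s = σ√(2(1 − ρ)), σ² = ln(1 + CV²) and ρ is the correlation of the log values. With ρ = 0 and CV 15%, 25%, 35%, the excess is 1.4%, 4.9%, 8.9% at r = 0.8 and 8.4%, 13.8%, 19.0% at r = 1.0. Correlation shrinks it: at r = 0.8 and CV 25%, 4.9% becomes 2.2% at ρ = 0.5 and 0.5% at ρ = 0.8. At r = 0.6 and CV 15% it is 0.0%.

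**Day 736.** If only the EOI-only patients lose the 1-hour value, the pooled geometric-mean loss is 1 − exp(−E × 9/28) or 1 − exp(−E × 3/28). At the extreme, E = 0.2117, these are 6.6% and 2.2%. The subgroup's extra later samples can only push the other way.

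**4. A true rise.** With a true +20%, the observed change is 1.20 × exp(−E) − 1: +15.5% at r = 0.9, s = 0.2; +10.8% at r = 1.0, s = 0.2; and −2.9% only at the extreme corner, r = 1.1, s = 0.4.

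**5. Day list.** Adding 1 to the scheduled routine PK days after the first dose gives 22, 43, 64, 85, 169, 274, 358, 463, 547, 652 and 736. Ten of the 11 match. Listed Day 463 is D462, whose column in Table 1-2 is shared with D651 (651/30.44 = 21.4 months), so the Month-21 visit is SAP Day 652. Listed Day 673 is D672 (22.1 months), which shares a column with D483. SAP 4.5.2 also assigns the Month-24 profile parameters to Day 726, whereas that profile is on Day 736.

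**The case against.** **The EOI series is already planned.** SAP 4.5.2 summarises plasma concentrations at each nominal time, with individual plots and by-subject listings, so a careful reader could see whether a step in Cmax is a sampling artefact. The protocol also plans population PK modelling of rich and sparse samples, and refers PK detail to a separate analysis plan that is not among these documents. This stands as mitigation, but it does not correct the Cmax table or the plots that use Cmax.

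**Stakes are modest.** PK is a tertiary objective, no hypothesis is tested, and no accumulation ratio or year-to-year comparison of Cmax is specified. This stands, and it is why only a small change is proposed.

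**The artefact may be nil.** If concentration always peaks at EOI, nothing is lost. Nothing in the documents supports a 1-hour/EOI ratio near 1, which the larger figures need. That also stands. But the SAP applies Cmax to three analytes and tabulates Tmax at the rich profiles, so it does not itself presume a peak at EOI.

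**Stronger readings do not hold.**

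- A reader might infer that Year 2 Cmax can only fall or stay level. That is true only for an unchanged profile; step 4 shows real increases coming through.
- A reader might infer that the 1-hour sample ends with Year 1. It does not for the PK/PD subgroup at Month 24, the planned majority of patients.
- A reader might infer that the mixed models inherit the problem. SAP 4.5.2 says only that such models may be used for exposure to ALN-18328 and does not name Cmax there; nor does it say which visits' Cmax enters the plots.

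**Conclusion.** The point holds in a limited form. As written, the SAP's Cmax series mixes a two-sample maximum (Year 1), a single post-infusion value (sparse Year 2 visits) and, on Day 736, a pool of six-sample and one-sample values. Under unchanged pharmacokinetics the sparse Year 2 values are biased down or unchanged against Year 1.

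The sampling difference and its direction follow from the documents alone. The size does not: about 0% to 19% rests wholly on assumed values (r from 0.5 to 1.1, s from 0.1 to 0.4), is 4.0% or less if the 1-hour level is typically 50–70% of EOI, and shrinks as correlation between the two samples grows. The tables could show a step after Year 1; the documents do not establish that they would. The change is worth making because it is cheap and removes the artefact whatever its size.

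**What to change.** In SAP 4.5.2:

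1. Base the by-visit series on the EOI concentration, or on a Cmax restricted to the common times (pre-dose and EOI). EOI is scheduled at every routine PK dosing visit in both years and in the Month-24 rich profile. On common times the artefact is 0% at every visit.
2. Use the same quantity in the exposure-response plots, and in any mixed model that would use Cmax.
3. Keep observed Cmax and Tmax for the PK/PD subgroup's rich profiles: Day 1, Day 232 and the Month-24 profile.
4. Reconcile the day list with the schedule. Day 673 has no scheduled routine PK sample, since the Month-21 PK visit is D651 (SAP Day 652); the column of the plasma PK mark should be confirmed in the typeset Table 1-2. Day 726 should be reconciled with the Day 736 profile.

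The cost is SAP wording and one table shell, with no new samples. The one loss is that a peak after EOI at a routine Year 1 visit no longer enters the by-visit series; it remains visible in the planned summaries by nominal time and in the listings.
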